5.4. Intervention

5.4.1. Aim 1: Alcohol reduction intervention

We will compare an economic incentive-based intervention, to no incentives, in order to promote reductions in heavy alcohol use over six months of IPT in HIV/TB co-infected adults. In the Aim 1 intervention arms, participants will be told at baseline and at each study visit that each time they come to a monthly IPT refill visit and have a negative urine EtG test (detects alcohol consumption), they will instantly win a prize by drawing a lottery scratch card. Prize types and probabilities of winning a low, medium, or high-valued prize are described in section 5.4.3. The number of lottery scratch cards awarded per participant will increase by one card at each subsequent visit with a negative urine EtG results, thereby providing an escalating prize incentive (best practice for incentive-based interventions^{2,147,148}) for sustained reductions in alcohol use (see Figure 2).

If a participant has a positive urine EtG test, no lottery scratch cards will be given for alcohol use reduction, and the participant will “reset” to drawing one lottery card if the urine is EtG negative at the subsequent visit. Escalating incentives with a “reset” were chosen to offer greater reward for continuous, rather than intermittent, reductions in alcohol use over the full six months of IPT, so as to minimize risk of hepatotoxicity on INH.²⁷ INH refill visits will be scheduled at the beginning of the week whenever possible, as our previous data show that the majority of heavy drinkers use alcohol during weekend days.

Figure 2. Example of escalating prize incentive for participant enrolled in

5.4.2. Aim 2: INH adherence intervention

We will compare an economic incentive-based intervention to promote adherence to INH during six-months of IPT, to no incentives. Similar to Aim 1, in the Aim 2 incentive-based intervention, participants will be told at baseline and at each study visit, that each time they come to a scheduled clinic visit and have a positive urine IsoScreen (INH) test, they will have a chance to instantly win prizes by drawing a lottery scratch card that will reveal a low, medium or high value prize. The Aim 2 escalating prize incentive design will be identical to the Aim 1 incentive design, to avoid confusion among participants and research assistants, and simplify trial implementation.

Briefly, the number of scratch card draws allowed per participant will increase by one at each subsequent visit with positive urine IsoScreen results, and a negative urine IsoScreen will result in no lottery scratch cards at that visit, with a “reset” (i.e. one scratch card drawn) at the subsequent visit. Prizes and probabilities of winning medium and high-value prizes will be as in Aim 1, and are described below. Those randomized to both Aim 1 and 2 incentive interventions (persons in Arm 4) will be eligible to receive lottery card draws separately for each test (i.e. prizes awarded independently).

5.4.3. Prizes

Prizes will be chosen during a preparatory phase in consultation with community members and clinic staff at each site. The value of the prizes will reflect a balance between cultural acceptability, cost (i.e. scalability), and efficacy. Prizes that are too low in value may be dismissed as insufficient to reinforce reductions in heavy drinking or INH adherence,¹⁴⁹ and several studies have demonstrated that increasing the magnitude of a reward can result in greater uptake of a desired behavior.^{43,150,151} However, using prizes that are too high in value could limit scalability of the proposed interventions to real-world clinical settings, and be perceived as coercive. On this basis, we will limit low-value prizes to no more than US\$5, representative of one week's worth of wages in rural Uganda.¹⁵² We will limit high-value prizes to no more than ten times the low-value amount (US\$50).¹⁵¹ The value of medium value prizes will range between the low and high-value amount, and the probabilities of winning will range from 1-5% for high-value prizes and 5-10% for medium-value prizes. All lottery scratch cards will have at least a low-value prize (guarantee of winning). Past prizes used in our studies have included cell phone airtime (low value), T-shirts (medium value) and cell phones (high value). We will reinforce the incentive system at each INH refill visit verbally and using visual aids, similar to those we ([name], [name]) are using in an ongoing study of escalating incentives for HIV virologic suppression in southwestern Uganda (R01 MH105254; NCT:02890459).

5.4.4. Aim 3: Impact assessment of intervention

At month 12 (6 months after the Aims 1 and 2 trial completion), we will perform a study interview with participants regarding their health and alcohol use, measure PEth levels and plasma HIV viral load, and conduct TB case-finding through symptom screening, with follow-up chest x-ray and/or sputum MTB/RIF Xpert assay for symptomatic persons (Table 2).

5.5. Study visits

As previously described, eligibility will be a two-stage process in order to determine drinking status, TST status, and rule out active TB and liver enzyme elevations. Baseline visits will include collection of tracking information, a baseline survey (Table 2), blood draw, and repeat liver enzyme testing if it has been longer than one month from the screening tests.

[figure not shown]
Visits for INH refills and assessments for toxicity (assessment of side effects and liver enzyme testing) will occur at week 2 and months 1 through 6 for all study participants. Urine will be collected and prizes administered as described above for Arms 2, 3, and 4. Hair collection will occur at 3 and 6 months c at the time of the INH discontinuation if outside of the 3- and 6-month time point for all study participants (see below). Follow-up interviews and blood collection will occur at months 3, 6, and 12 (Table 2). Screening for symptoms of active TB, and sputum testing and chest X-ray if symptoms are reported, will occur at every follow-up visit.

Arms 2-4 only: Urine test(s) and prize(s)
↓
Month 12: Study survey, Blood draw (PEth, VL)

Retention: High retention (90% at six months, 85% at one year) will be maintained as in our prior studies using follow-up phone calls, alerts when patients come to their home clinic, and home visits when needed. To encourage high retention, participants in all study arms, including control, will receive travel reimbursements (low-value unconditional cash transfers) of up to US\$5 for attending study visits (see Figure 3).

Missed or late visits: If a participant misses a scheduled visit, the visit will be rescheduled within the coming 4 weeks after the missed visit, and missed visits (i.e. no-show for a clinic appointment >3 days after the scheduled clinic appointment date) will automatically prompt an incentive “reset” to baseline (i.e. drawing one card only if the incentive condition is met). Late or early visits, defined as coming to an appointment more than 3 days of an assigned appointment date, will result in an incentive “reset” to baseline. On rare occasion, exceptions to the protocol for early, late, and missed visits may be considered at the discretion of the study coordinator and study PIs. All participants will be allowed up to 9 months from INH initiation to complete a 6-month course (180 tablets) of INH, taking missed visits/refills into account. Participants that miss ≥3 months of visit time will be considered as having failed to complete IPT.

Figure 3. Study visit flow chart: Aims 1, 2 & 3.

5.6. Specimen collection and laboratory procedures

Specimen processing, storage, and shipment: Initial specimen processing will be conducted at the [MUST Clinical Laboratory \(DIPT 1/2\)](#), and [SEARCH laboratories \(DIPT 2/2\)](#), or other affiliate laboratories in Southwestern Uganda, with quality assurance checks instituted for correct labeling of the specimens and temperature maintenance of the freezers. We will build upon the specimen tracking and inventory application used for Uganda ARCH study. Specimens will be transferred to the US for PEth testing at the United States Drug Testing Laboratories (USDTL), and for hair testing at UCSF. The laboratory testing (ALT/AST, CD4 count, sputum testing, hepatitis B surface antigen [HBsAg], and HIV viral load) will be conducted onsite in Uganda.

Blood testing: Blood will be collected at baseline, 3, 6, and 12 months for testing as noted above.

- a) **PEth:** DBS will be spotted from venous blood samples onto Whatman 903 filter paper, stored at -80°C to promote stability, and shipped in batches to the United States Drug Testing Laboratories, where the PEth level will be determined using LC/MS-MS for the 16:0/18:1 homologue as described.¹⁵³ We will obtain a Materials Transfer Agreement to ship the DBS to the U.S.; no laboratories in Africa conduct this test.
- b) **HIV viral load:** Plasma HIV viral load will be measured using the Cepheid Xpert HIV-1 RNA assay, run on an existing GeneXpert platform in Mbarara, Uganda, that has been in use for our ([name], [name]) ongoing incentive trials. This assay has been validated relative to the Abbott RealTime HIV-1 assay.^{154,155}
- c) **Liver enzymes (ALT and AST):** Same day testing will be performed for safety of providing INH refills.

Urine EtG and IsoScreen testing methods: At each INH refill visit, participants in Arms 2, 3, and 4 will be asked to provide a urine sample in a sterile cup. The urine will be received by a RA, who will check that the urine is between 32°C and 40°C (to confirm lack of tampering), and conduct the EtG dipstick test (Arms 2 and 4) and/or the IsoScreen test (Arms 3 and 4). Urine EtG screening at the study eligibility visit will be collected and temperature checked in the same fashion.

Urine pregnancy testing: For women of childbearing age, their screening visit urine sample will be used to test for pregnancy. Women who are pregnant at the screening visit will be excluded from the trial. Women who enroll into the trial will be asked at each follow-up visit whether they may have become pregnant. Those who answer yes will be provided a urine pregnancy test following the same procedures as the screening test.

Hair testing: INH concentrations will be measured in hair samples in all participants at 3 and 6 months. Hair collection methods have been outlined in previous papers.^{117,135,156} We will request that participants do not shave or cut their hair for one month prior to their 3- and 6-month visits; in the case that a participant does not have enough scalp hair to collect, we will schedule the participant for a hair collection visit 3-4 weeks later. Hair samples will be kept at room temperature and in a dark place prior to batch shipment (without biohazardous restrictions) to the Hair Analytical Laboratory at UCSF for INH measurement as described above.

Table 2. Schedule of study specimen and data collection.

	Eligibility	Baseline	Week 2	Month 1	Month 2	Month 3	Month 4	Month 5	Month 6	Month 12
ALT and AST testing	◆		◆	◆	◆	◆	◆	◆	◆	
CD4 count, hepatitis B surface antigen, platelet count, creatinine	◆									
HIV viral load	◆								◆	◆
Urine EtG (All Arms at Eligibility; Intervention Arms 2+4 thereafter)	◆		◆	◆	◆	◆	◆	◆	◆	

Urine IsoScreen (Intervention Arms 3+4)		◆	◆	◆	◆	◆	◆	◆
Urine Pregnancy test (women)*	◆	◆	◆	◆	◆	◆	◆	◆
INH MEMS cap data download		◆	◆	◆	◆	◆	◆	◆
Hair collection for INH level					◆			◆
DBS for PEth testing		◆			◆		◆	◆
Study interview		◆			◆		◆	◆
Assessment for active TB (symptoms, chest X-ray, Xpert if symptomatic)	◆		◆	◆	◆	◆	◆	◆

*Pregnancy test given to all women at Screening, and as-needed at follow-up visits (based on self-reported potential pregnancy)

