For alcohol, the abnormal phospholipid phosphatidylethanol (PEth) is formed only in the presence of alcohol, and is therefore highly specific. PEth has an estimated half-life of 4-12 days, indicating that it will be positive several weeks after heavy drinking.⁷⁵ PEth has shown >95% sensitivity and 100% specificity in comparisons of patients entering alcohol treatment compared to abstainers and light drinkers,⁷⁶⁻⁷⁹ and several studies have shown correlations of PEth with cumulative measures of alcohol consumption of >0.70.⁷⁵ PEth is now an endpoint in alcohol treatment trials.^{80,81} PEth can be measured from dried blood spots (DBS) that are easy to store, non-infectious, and easy to transport.

For IPT adherence, INH in small hair samples captures INH adherence over a period of weeks to months, and is an innovative biometric to assess long-term adherence/pill-taking.⁸² We ([name]) have validated a method to analyze INH in small scalp hair samples using liquid chromatography/tandem mass spectrometry (LC/MS-MS).⁸² We have examined INH levels in the hair of adults on directly observed daily IPT; all had detectable INH levels with a median of 7.6 ng/mg

(inter-quartile range (IQR) 4.7-11.8).⁸² Like DBS, hair is non-infectious, and easy to store and transport. As of the date of this submission, studies of clinically meaningful cut-points for INH hair levels are in progress but not completed. Thus we will use MEMS-measured bottle openings, the current reference standard for adherence,⁸³ as our primary outcome measure for Aim 2, and include INH hair concentration, an emerging biologic marker of IPT adherence, as a secondary outcome.

Understanding whether short-term interventions to reduce heavy alcohol use and promote medication adherence impacts long-term HIV virologic suppression is needed. In a recent analysis of individual-level predictors of having a detectable viral load among 8,828 HIV-infected adults in the SEARCH study (see Preliminary Studies), binge drinking (>5 drinks per occasion) was associated with increased odds (adjusted Odds Ratio (aOR): 1.62, 95% CI: 1.28-2.05) of detectable viremia.⁸⁴ In another prospective cohort of persons prescribed ART in Uganda, problem alcohol use was the strongest predictor of increased odds of viral failure; the association was mediated through reduced ART adherence.³³ Therefore, interventions to increase ART adherence and thereby increase viral suppression in heavy drinkers in SSA are urgently needed.

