An exploratory outcome for Aim 2 will be drug concentration (ng/mg) in a subset of small hair samples. Hair levels of INH measure long-term and cumulative exposure to INH will be used to determine if short-term increases in adherence translate to sustained changes in behavior.

Intervention-by-time-interaction. For Aims 1 and 2, we will check for the presence of intervention-by-time interaction by conducting separate analyses at months 3 and 6. We will use generalized estimating equations with an independent working correlation matrix for binary outcomes and random effect models for continuous outcomes.

Impact of COVID-related disruptions. Recruitment started on April 16 2018 and study activities were paused in March 19, 2020 due to a lockdown enforced by the Ugandan government in response to the COVID-19 pandemic. During this time, all research activities were stopped and participants on INH were contacted and instructed to stop taking their INH pills immediately, as there were no means to effectively monitor for liver toxicity. Study visits resumed on May 26, 2020 and enrollment resumed on June 16, 2020. We will conduct several descriptive statistics to examine to what extent the lockdown and the pandemic might have impacted the generalizability of the trial's findings. First, we will group the participants based on whether their scheduled INH completion date was before versus on or after March 19 2020 and will compare their baseline characteristics including measures of drinking. Second, we will perform an analysis to explore whether completion of INH before or after pandemic interruption acts as potential effect modifier of the incentive interventions.

Subgroup analyses. We will perform analyses to explore potential effect modifiers of the incentive interventions. For Aims 1 and 2, the potential moderators of interest are: sex, baseline level of alcohol use, time and risk preferences, and readiness to change . For each aim, we will fit separate models including 2-way interactions between randomization group and each potential effect moderator, as well as a model testing the interaction between the two

interventions. If an interaction is significant, subsequent stratified analyses will be conducted to explore the effect of the economic incentive interventions by categories of the moderator.

References

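### At month 6 the 3-4 week hair re-collection falls after the INH course for on-time completers, so those samples can read falsely low

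*Protocol*

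**What the plan says.** Protocol section 5.6 (Hair testing) plans that "INH concentrations will be measured in hair samples in all participants at 3 and 6 months". To secure enough hair it adds: "We will request that participants do not shave or cut their hair for one month prior to their 3- and 6-month visits". If there is still too little, "we will schedule the participant for a hair collection visit 3-4 weeks later". One rule covers both visits, with no exception for month 6.

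On the length of the course, Protocol section 5.5 states: "All participants will be allowed up to 9 months from INH initiation to complete a 6-month course (180 tablets) of INH". The same section also has hair taken "at the time of the INH discontinuation if outside of the 3- and 6-month time point for all study participants". It does not say what happens if hair is too short on that occasion.

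Section 3 of the protocol explains the purpose of the measure: "INH in small hair samples captures INH adherence over a period of weeks to months". Protocol sections 5.7.1 and 5.9.2 treat hair level as a continuous secondary outcome. The SAP, under Exploratory analyses, reduces its role: "An exploratory outcome for Aim 2 will be drug concentration (ng/mg) in a subset of small hair samples". It does not define the subset, and it has no rule on samples taken after INH has ended.

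**The concern.** Hair level is meant to reflect exposure over the weeks to months before sampling. The request not to cut hair for a month, and the collection at discontinuation, both tie the sample to growth while INH is being taken. The month-6 fallback breaks that tie for participants who finished on time, because the growth it waits for comes after the last scheduled dose.

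Hair is the only long-window measure of ingestion in the plan; MEMS records bottle openings. A falsely low value in someone who took every dose lowers the month-6 levels and widens their spread, and it could look like disagreement with MEMS. The error may also differ between groups. Punctual completers are exposed to it and late participants still on INH are not, so if incentives improve on-time completion it would tend to shrink a true incentive effect.

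**Working it through.** The plan states no figure that depends on this rule, so there is nothing to reproduce.

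**Inputs from the documents.** Delay of 3-4 weeks, i.e. 21-28 days (Protocol 5.6). Course of 180 tablets over 6 months, up to 9 months allowed (Protocol 5.5). Under directly observed daily dosing, "all had detectable INH levels with a median of 7.6 ng/mg", with interquartile range 4.7-11.8 (Protocol 3). No established hair cutoff for adherence (Protocol 3.1).

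**Step 1: dates.**
- Month 6, on time: 180 + 21 = day 201 to 180 + 28 = day 208, so 21-28 days after the last scheduled dose.
- Month 3: 90 + 21 = day 111 to 90 + 28 = day 118, at least 62 days before day 180 and so still on drug.
- A participant whose course runs beyond day 208 is still on INH at the month-6 re-collection.

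**Step 2: dilution (illustrative).** Let k be the weeks of on-drug growth already present at month 6 (assumed 0-4) and w the 3 or 4 weeks of later growth. Assume even growth, assay of the whole length, and no lag or washout. The on-drug share is k/(k + w), and a true level of 7.6 ng/mg reads 7.6 × k/(k + w).

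| k | w = 3: share, reading | w = 4: share, reading |
|---|---|---|
| 0 | 0%, 0 | 0%, 0 |
| 1 | 25%, 1.90 | 20%, 1.52 |
| 2 | 40%, 3.04 | 33%, 2.53 |
| 3 | 50%, 3.80 | 43%, 3.26 |
| 4 | 57%, 4.34 | 50%, 3.80 |

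The sample is wholly off drug only when k = 0. In every row a participant at the observed-dosing median reads below that group's lower quartile of 4.7.

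**Step 3: spread.** Log SD under observed dosing = ln(11.8/4.7)/1.349 = 0.682. If a share f of month-6 samples reads m-fold low, independently of the true level, the log variance becomes 0.682² + f(1 − f)(ln m)². Information kept is the inverse of the variance ratio. Both f and m are assumptions.

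| f | m = 3: ratio, information kept | m = 10: ratio, information kept |
|---|---|---|
| 5% | 1.12, 89% | 1.54, 65% |
| 10% | 1.23, 81% | 2.02, 49% |
| 20% | 1.41, 71% | 2.82, 35% |

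The log SD is also an assumption for this trial, because participants dose themselves and should vary more. For f = 10% and m = 10, a log SD of 1.0 gives 1 + 0.477/1.00 = 1.477, or 68% kept. A log SD of 1.5 gives 1 + 0.477/2.25 = 1.212, or 82.5% kept.

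**Step 4: bias between groups.** The mean log level in a group shifts by −f × ln m, and equal shares cancel in the comparison. If one group had 5% affected and the other none, the shift would be 0.05 × ln 3 = 0.055, about 5% on the geometric mean. For a ten-fold drop it would be 0.05 × ln 10 = 0.115, about 11%.

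**The case against.** The strongest reply is that few samples are involved and little depends on them. Protocol 3.1 reports acceptability and feasibility above 95% for hair collection in African settings, including short, previously shaved hair, and section 6.1 says short hair is usually no obstacle. These figures come from other studies, but they point to 5% or fewer. The SAP makes hair exploratory, in a subset, and names no month-6 comparison. This reply stands and limits the size of the point. It does not supply the missing rule.

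A reader might infer several stronger things that the documents do not support:
- **That the re-collected hair is all off drug.** Short hair present at month 6 grew on drug, so many samples would be mixed, and the assayed segment is not stated. On the other side, if short hair is usually collectable, the fallback would mostly be used when hair is almost absent.
- **That adherent participants would be classed as non-adherent.** No cutoff exists and the protocol analyses the level as continuous. The value can only be said to read falsely low.
- **That about half the information is lost.** That needs 10% affected, a ten-fold drop and the spread seen under observed dosing, all together.
- **That the same fallback causes off-drug samples at early discontinuation or after the lockdown.** Section 5.6 ties the fallback to the 3- and 6-month visits. Study visits stopped on March 19, 2020 and resumed on May 26, 68 days later. Hair taken afterwards from someone told to stop INH may be off drug, but not because of the 3-4 week rule.

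**Conclusion.** The point holds in a limited form. For a participant who completes on time, the stated rule places the re-collected month-6 sample 21-28 days after the last scheduled dose, where it can read falsely low, and neither document flags or sets aside such samples. The dates follow from the documents alone.

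The size does not. The number affected, the amount of on-drug hair present, the segment assayed and the spread in this trial are all unstated. At the share the protocol's experience suggests (5% or fewer), the loss of information runs from about 11% for a three-fold drop to about 35% for a ten-fold drop, with the spread seen under observed dosing; wider spread makes it smaller. A bias toward no incentive effect is possible but rests on incentives changing on-time completion. Month-3 hair and the MEMS primary outcome of Aim 2 are unaffected.

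**What to change.** **Procedure (Protocol 5.6).** Use the delayed re-collection only if the participant will still be prescribed INH on the re-collection date. That keeps it at month 3, and at month 6 only where the course is unfinished. Otherwise record the hair sample as missing, not as a low level. Use the existing month-5 visit to remind participants not to cut their hair.

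**SAP.** Record the days from the end of prescribed INH to hair collection. Exclude from the main hair analysis, or analyse separately, samples taken more than a pre-set number of days after that end. Define the end as completion of the course or an instructed stop, including the lockdown stop.

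Do not key the rule to the last MEMS opening. Someone who stopped opening the bottle in month 5 and gave hair on time at month 6 has a correct low value. Dropping that value would select on the behaviour Aim 2 is meant to change and would conflict with the intention-to-treat principle in Protocol 5.9.

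**Cost.** About one sentence in the procedure and two in the SAP, plus recording of the collection date and the end of prescribed INH. A few month-6 values become missing, mostly in on-time completers, so report how many in each arm.
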